1.6. Study objectives

There is a growing need for safe and efficacious treatment of brain metastases. However, evidence for optimal treatment of larger brain metastases is poor. The current gold standard for radiotherapy of brain metastases between 1 - 4 cm is single-session radiosurgery (SRS), as defined by RTOG 9005. However, available evidence suggests that fractionated stereotactic radiotherapy (FSRT) could be significantly superior in terms of local control and toxicity in this subset of larger brain metastases.

Fractionated stereotactic radiotherapy (FSRT) is routinely used in clinical practice but has never been tested against single-fraction radiosurgery (SRS) in a randomized controlled trial so far. This study was therefore designed to determine whether FSRT with a dose of 12 x 4 Gy and a 2-mm safety margin is superior to single-fraction SRS according to RTOG 9005 criteria (gold standard) for the treatment of large brain metastases in terms of tumor control. CNS side effects especially radiation necrosis will be evaluated as secondary objectives.

1.6.1. Primary objective

Improvement of local control in patients with large brain metastases treated with fractionated stereotactic radiotherapy (FSRT) versus single-fraction stereotactic radiosurgery (SRS) according to RTOG 9005 guidelines (gold standard)

Primary endpoint: Time to local progression - TTLP

Local progression will be defined according to the *RANO-BM* criteria by an increase of at least 20% in the longest diameter of the metastasis relative to nadir or baseline. In addition to the relative increase of 20% the lesion must increase by an absolute value of 5 mm or more (Lin et al. 2015). True local progression and radionecrosis are differentiated via a prespecified algorithm in the trial (see Section 8.3.).

If multiple metastases are treated in the trial, progression is defined as at least one metastasis fulfilling the criteria for progression.

1.6.2. Secondary objectives

- Improvement of the tolerability of local radiotherapy, as measured based on the endpoints CNS toxicity and, in particular, radiation necrosis in accordance with the Common Terminology Criteria for Adverse Events Version 5.0. Improved tolerability will also be measured as time to radiation necrosis.
- Improvement of the local control of irradiated brain metastases, as determined based on volumetric criteria. Volumetric criteria may have

important methodological advantages over traditional endpoints for the identification of treatment failure, especially in the case of large brain metastases. This study aims to improve our understanding of volumetric criteria and helps to further establish them.

Based on the *RANO-BM* criteria, progression is defined as an increase in volume of 72.8% or more (corresponds to a 20% increase in diameter for a perfect sphere). True local progression and radionecrosis are differentiated via a prespecified algorithm in the trial. If multiple metastases are treated in the trial, progression is defined as at least one metastasis fulfilling the criteria for progression.

- Assessment of quality of life (EORTC QLQ-C30 and QLQ-BN20)
- Improvement of local progression-free survival
- Improvement of overall survival
- Improvement of brain metastases-specific survival
- Time to distant brain failure

1.6.3. Translational research projects

- Differentiation of radiation necrosis from recurrent tumor based on conventional MRI-imaging using advanced pattern-recognition and machine learning techniques (*Radiomics* project: *DEEP-CER-DIFF*).
- Correlation of *individual radiosensitivity* and radiation-related toxicity especially radionecrosis after stereotactic radiotherapy of brain metastases.
- *Detailed Immunophenotyping* to investigate systemic immune reactions following stereotactic radiotherapy of brain metastases.

See also section 1.5.

2. Study design

2.1. Type of study

Investigator-initiated, multicenter, open, randomized controlled phase III superiority trial.

2.2. Sample size calculation

On the basis of available retrospective and dose-response relationship data, it is expected that SRS will result in a 12-month local tumor control rate of approximately 65% and that FSRT can increase this rate to about 80% (cf. Section 1.4.). This difference is considered to be clinically significant. A sample size of N=191 evaluable cases each in the experimental and control arm, respectively, corresponding to a total of 382 patients, is required to detect a significant difference i.e. an increase in TTLP at least this large at 12-month follow-up in a randomized comparison (see Section 10.2.). The number of TTLP events to be observed is 82.

2.3. Scope of the study

This is a multicenter study.

2.4. Time schedule

Start of study:	Q3 2020
Start of recruitment:	Q1 2021
Duration of recruitment:	3 Jahre
Duration of follow-up:	2 Jahre
End of study:	2026

Follow-up is performed for progression/radionecrosis as well as for overall survival, toxicity and distant progression, respectively. In case of local progression, radionecrosis or distant progression, follow-up for the other events as well as toxicities and overall-survival continues. In case of radionecrosis, follow-up for progression continues, if not determined by histology, as progression can occur after a lesion has experienced radionecrosis. Conversely, in case of progression, follow-up for radionecrosis for the respective lesion ends.

3. Selection of study population

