7.2. Principles of Assessment

Differentiation between radionecrosis and local progression:

Following stereotactic radiotherapy, it can be difficult to differentiate true tumor progression from radiation necrosis (Chao et al. 2013, Lin et al. 2015, Soffietti et al. 2017). Frequently, a definitive differentiation is only possible with longer imaging follow-up or histologic diagnosis. Due to the large initial size of metastases included in this trial, surgical resection, if possible, constitutes the best diagnostic and therapeutic approach in the case of sustained or symptomatic enlargement and is therefore generally encouraged. As recommended in the *RANO-BM* guidelines, an algorithm (see Section 8.3.) is prespecified in the FSRT Trial to provide differentiation between radionecrosis and progression and enable standardized management in the case of an enlarging lesion.

Criteria used for assessment:

The *RANO-BM* criteria are used in the FSRT Trial for the definition of progression (Lin et al. 2015). As the assessment of local control is the primary aim of the FSRT Trial, only lesions treated as part of the trial are used for the definition of progression in accordance with the *RANO-BM* guidelines for localized therapy trials. For the same reason, corticosteroid use, and clinical status are not used for the definition of local control in this trial.

Assessment if multiple brain metastases are treated in the FSRT Trial:

If multiple brain metastases are treated in the FSRT Trial, local control or radionecrosis will first be determined for each metastasis treated in the trial according to the criteria described in 7.3. and the algorithm for the differentiation between radionecrosis and progression provided in 7.4. If at least one metastasis fulfills the criteria for progression or radionecrosis, this is scored as an event, i.e. as progression or radionecrosis event on a patient

level. If at least one metastasis fulfills the criteria for progression and at least one fulfills the criteria for radionecrosis, this is scored as both a progression and a radionecrosis event on a patient level. This definition is used as it is better suited for the assessment of efficacy and tolerability of multiple local treatments than a combined metric.

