If the patient shows neurologic symptoms that are resistant to glucocorticoid treatment or if the patient is symptomatic and glucocorticoid treatment is contraindicated, resection of the enlarging lesion is advised. Resection will provide definitive histologic diagnosis. Histology will be classified as "radionecrosis", "viable tumor" or "both" as has been done in the RTOG 9005 trial (Shaw et al. 2000). In the case of radionecrosis, this will be scored as radionecrosis event, in the case of viable tumor, this will be scored as progression event and in the case of viable tumor and radionecrosis, this will be scored as both radionecrosis and progression event. The time of the respective event will be backdated to the first imaging showing an increase in largest diameter of at least 20% and 5 mm or more. If resection is not possible or if the patient denies surgery, stereotactic biopsy is recommended. Scoring will be performed as mentioned for resection. If stereotactic biopsy is not possible, an amino acid or FDG-PET coregistered to MRI is recommended. In the case of findings suggestive of radionecrosis on amino acid or FDG-PET a trial with Bevacizumab is advised according to Levin et al (Levin et al. 2011, Chao et al. 2013, Soffietti et al. 2017). Imaging intervals should be shortened to 6 weeks or less. If the metastasis shows regression after initiation of bevacizumab or corticosteroids or regresses spontaneously during subsequent imaging follow-up back to baseline or nadir diameter or shows a relative decrease in the longest diameter of at least 30% compared to the maximum size during enlargement, this will be scored as radionecrosis instead of progression. Else if the lesion receives additional treatment, i.e. Whole brain radiotherapy, repeat stereotactic radiotherapy or systemic treatment with established CNS effect, if the patient dies or is lost to follow-up or if routine study follow-up ends, this is scored as progression and the time of the event will be backdated to the first imaging showing an increase in largest diameter of at least 20% and 5 mm or more.

No Glucocorticoid-resistant symptoms:

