9.1. Research question and hypothesis

The primary research question to be answered in this randomized controlled trial is whether FSRT (experimental arm) achieves significantly better local control than the "gold standard", single-fraction SRS (control group) in patients with large brain metastases. The time to local progression (TTLP) of the irradiated lesions will be used as the primary endpoint for efficacy. TTLP is defined as the time from randomization until the detection of progression as per the *RANO-BM* criteria (cf. Section 8.1 – 8.3). Patients will be censored if they have no signs of local progression at the time of last tumor monitoring during follow-up or at the onset of one of the following competing risk events not associated with, or preceded by local progression: death, lost to follow up, unauthorized non-protocol treatment of the target lesions. The following hypotheses will be tested:

H0: HR (FSRT vs. SRS as standard) ≥ 0

H1: HR (FSRT vs. SRS as standard) < 0

HR = Hazard ratio

One-sided testing of the primary endpoint will be performed based on the formulated hypotheses.

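### Section 2.4 ends progression follow-up after any histologic radionecrosis, although a biopsied lesion stays in place and can still progress; the numerical effect on TTLP is small

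*Protocol*

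**What the plan says.** Protocol Section 2.4 (Time schedule) has three consecutive sentences on this.

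- General rule: "In case of local progression, radionecrosis or distant progression, follow-up for the other events as well as toxicities and overall-survival continues".
- Exception: "In case of radionecrosis, follow-up for progression continues, if not determined by histology, as progression can occur after a lesion has experienced radionecrosis".
- Mirror rule: "Conversely, in case of progression, follow-up for radionecrosis for the respective lesion ends".

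Section 7.4 gives two routes to histology. Resection comes first, and then: "If resection is not possible or if the patient denies surgery, stereotactic biopsy is recommended. Scoring will be performed as mentioned for resection". Sections 7.3 and 7.4 also allow a specimen to show radionecrosis and viable tumor together, scored as both events.

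TTLP is a patient-level endpoint: progression of at least one treated metastasis counts (Sections 1.6.1 and 7.3). Section 7.2 assesses each treated metastasis separately and then states: "If at least one metastasis fulfills the criteria for progression and at least one fulfills the criteria for radionecrosis, this is scored as both".

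Section 9.1 censors patients who have no local progression at their last tumor assessment, or at one of these events: "death, lost to follow up, unauthorized non-protocol treatment of the target lesions". Histologic radionecrosis is not on that list. The note to the enlarging-lesion flow chart, after the synopsis, says that once progression/radionecrosis follow-up ends, survival, toxicity and distant progression are still followed. It does not mention local progression.

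**The concern.** The exception in 2.4 makes sense for a lesion that has been removed. It is worded for any lesion with a tissue diagnosis. After biopsy the irradiated lesion is still there and still measurable. The reason given for continuing after imaging-defined radionecrosis, that progression may come later, applies to it unchanged. Because the protocol accepts that necrosis and viable tumor can coexist, a sample showing necrosis does not prove that the rest of the lesion cannot progress.

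The second problem is scope. The mirror rule is tied to the lesion concerned; the exception is not. With up to 10 metastases per patient and an any-lesion endpoint, a site could take it as ending progression assessment for the whole patient. The last-assessment clause of 9.1 would then censor TTLP without histologic radionecrosis ever being named as a reason. The same happens under a lesion-level reading when the biopsied lesion is the only one treated.

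At stake is loss of primary-endpoint follow-up triggered by a treatment outcome. Section 1.3 expects less radionecrosis with fractionation, so the loss would fall more on the SRS arm. The trial is open (Section 2.1), so decisions to obtain tissue are made with the arm known.

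**Working it through.** **Text check.** For a completely resected lesion, the stop in 2.4 is consistent with its reason. For a biopsied lesion it contradicts that reason, and no other section corrects it. Section 7.4 returns radionecrosis shown by regression without glucocorticoid-resistant symptoms to routine follow-up, but has no matching statement for histologic radionecrosis. On scope, the reason in 2.4 (it speaks of a lesion), the mirror rule, the general rule and Section 7.2 point to the lesion; the missing qualifier and the flow-chart note leave the patient reading open.

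**Inputs from the protocol.** 12-month local control 65% (SRS) and 80% (FSRT); about half of patients dead by 12 months, exponential; 12-month follow-up; one-sided alpha 0.025; power 80%; 191 per arm (Section 9.2). Radionecrosis 5-20% after SRS of larger metastases (Section 1.5).

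**Assumptions, not in the protocol.** The 5-20% is reached by 12 months; FSRT has half the SRS rate; 25-50% of cases are proven by histology (100% as an upper bound).

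**Reproducing the plan.** Yearly hazards: λ1 = −ln 0.65 = 0.4308; λ2 = −ln 0.80 = 0.2231; mean λ̄ = 0.3270; loss η = ln 2 = 0.6931; HR = 0.2231/0.4308 = 0.518.

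Event probability: P(λ,η) = λ/(λ+η) × [1 − exp(−(λ+η))]. This gives 0.2587 (SRS) and 0.1461 (FSRT), so 191 × (0.2587 + 0.1461) = 77.3 events.

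Lachin-Foulkes, with φ = λ²/P: φ(λ1) = 0.7173, φ(λ2) = 0.3408, φ(λ̄) = 0.5216.

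N = {[1.960 × √(4 × 0.5216) + 0.842 × √(2 × 0.7173 + 2 × 0.3408)] / (0.4308 − 0.2231)}² = 381.5, or 191 per arm.

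The stated 382 is reproduced, with power 80.1%. The stated 82 events are not (77-78 here), but that is a separate matter and does not affect this check.

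**Patient-level stop, the less favourable reading.** With radionecrosis rate r and histology share h, the stop adds a loss hazard κ = −ln(1 − r·h). Patients cut short per arm: 191 × κ/(κ+λ+η) × [1 − exp(−(κ+λ+η))]. Events and power use η + κ in place of η.

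Example, r = 20% in SRS and 10% in FSRT, h = 50%: κ = 0.1054 and 0.0513. SRS patients cut short = 191 × (0.1054/1.2293) × [1 − exp(−1.2293)] = 11.6.

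| SRS radionecrosis | Histology share | Cut short SRS / FSRT | Events | Power |
|---|---|---|---|---|
| no stop | – | 0 / 0 | 77.3 | 80.1% |
| 5% | 25% | 1.4 / 0.8 | 77.0 | 79.9% |
| 5% | 50% | 2.9 / 1.6 | 76.7 | 79.7% |
| 20% | 25% | 5.8 / 3.1 | 76.0 | 79.4% |
| 20% | 50% | 11.6 / 6.3 | 74.7 | 78.7% |
| 20% | 100% | 23.4 / 12.6 | 71.9 | 77.3% |

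**Effect on the hazard ratio.** In a simulation at 20% and 50%, the progression hazard after radionecrosis was varied. If it doubles, the HR is 0.509 without the stop and 0.518 with it. If it halves, 0.524 and 0.519. If unchanged, 0.518 both ways.

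**The case against.** A reader might infer that 2.4 ends assessment of the patient's other treated lesions. The protocol does not state that. The general rule, the mirror rule and Section 7.2 all favour a lesion-level stop, and scoring both events in one patient presupposes that one necrotic lesion does not end assessment of the rest. What remains is an ambiguity.

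A reader might also infer that TTLP is censored at the biopsy or operation. Section 9.1 does not list that event; censoring would arise only through the last-assessment clause, once no treated lesion is being assessed.

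A third tempting step is to multiply 191 × 20% × 50% × 35% and report about 6.7 lost SRS events. That ignores deaths and the follow-up already used before radionecrosis. In the same setting the model loses about 2.1 SRS events (49.4 to 47.4) and 0.6 FSRT events. Nor is a bias against the trial's comparison shown: censoring removes time at risk along with events, and the small HR shift goes either way.

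Furthermore, Section 7.2 favours resection where possible and 7.4 makes biopsy the fallback, so many histologic cases would be resected lesions for which stopping is reasonable. The images would still be taken and uploaded.

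All of this limits the size and scope of the point. It does not answer the biopsy problem, which holds under either reading of 2.4.

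**Conclusion.** The point holds in limited form. As written, 2.4 stops progression assessment of a biopsied lesion that the protocol's own reasoning treats as still at risk, and it leaves unclear whether the stop concerns the lesion or the patient. Any loss would be linked to radionecrosis and so probably unequal between arms.

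The effect is small. Under the patient-level reading and the stated assumptions, about 1-12 SRS and 1-6 FSRT patients are cut short. Power falls by about 0.2 to 1.3 points (80.06% to 79.90% or 78.74%), at most 2.8 points if every case is histologic, and the HR moves by about 0.01. Biopsied lesions alone would have less effect. The histology share and the FSRT radionecrosis rate are assumptions, so the ranges are indicative. The point deserves correction because it is an avoidable, outcome-dependent gap in a primary-endpoint rule, not because it threatens the trial's result.

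**What to change.** Reword 2.4 so that:

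- progression assessment ends only for a lesion that has been completely resected with radionecrosis and no viable tumor;
- a lesion with biopsy-proven radionecrosis continues to be assessed for progression;
- all other treated lesions of the patient continue to be assessed.

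Align the flow-chart note and Sections 7.2 and 7.4 with this. State in 9.1 that histologic radionecrosis alone does not censor TTLP while any treated lesion remains under assessment.

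The cost is a wording change and continued central reading of these lesions. MRI is already scheduled at every follow-up visit to 24 months, and distant progression is followed in these patients anyway, so no extra scans are needed. The change concerns endpoint assessment only and alters no treatment.

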3.1. Inclusion criteria

1. Age \geq 18 years (no upper age limit)
2. Karnofsky Performance Scale (KPS) score $>$ 50
3. Life expectancy \geq 3 months
4. 1 to 10 brain metastases from a solid tumor except small cell lung cancer and germinomas
5. Indication for local radiotherapy of one or more brain metastases measuring 1 to 4 cm in longest diameter (measured in transversal, sagittal, coronal or oblique planes, the longest diameter measured in any plane counts)

6. Ability to understand the contents of the protocol and consent to participate, in writing
7. Written informed consent before enrollment in the study

3.2. Exclusion criteria

1. Whole-brain radiotherapy completed ≤ 6 weeks before study treatment or planned whole-brain radiotherapy following local radiotherapy
2. Prior radiotherapy of the metastasis or metastases to be irradiated in the present study
3. Relevant overlap of prior radiotherapy fields, cerebral or otherwise, with the metastasis or metastases to be irradiated in the present study
4. Location of metastasis to be irradiated in the brainstem.
5. Total of > 10 brain metastases, including previous metastases, at the time of inclusion in the study.
6. Cerebral metastases from small cell lung cancer or germinoma.
7. Contraindications to magnetic resonance imaging (e.g., metal implants, cardiac pacemaker, claustrophobia)
8. If a metastasis to be irradiated cannot be adequately differentiated in high-resolution, contrast-enhanced T1-weighted imaging for target volume delineation
9. Pregnant or nursing women
10. Women and men of reproductive age who are unwilling or unable to ensure highly effective contraceptive measures until 90 days following the last administration of radiation. (see 6.10 for details)
11. Chronic drug, medication or alcohol abuse
12. Psychological, familial, sociological, or geographical condition that would preclude study compliance
13. Nursing care patients
14. Inability to speak and understand German
15. Simultaneous participation in another clinical trial

4. Treatment plan

4.1. Indication for radiotherapy

The indication for radiotherapy will be determined according to the usual clinical standards or guidelines. The dose fractionation scheme, individual fraction size, total dose, and radiotherapy volume will be set in accordance with clinical standards and guidelines. The participating radiation oncologists will ensure each patient is able to receive radiotherapy according to protocol before he or she is included in the study.

4.2. Summary

Before the start of radiation treatment, each patient is randomly allocated to either fractionated stereotactic radiotherapy (FSRT = experimental arm) or to the "gold standard" treatment, single-fraction stereotactic radiosurgery according to RTOG 9005 (SRS = control arm). Randomization is stratified according to metastasis volume ($< 14.1 \text{ cm}^3$, $\geq 14.1 \text{ cm}^3$) and primary tumor histology (radioresistant histology: melanoma, renal cell carcinoma and sarcoma vs. other).

Single fraction stereotactic radiosurgery (SRS = control arm) will be performed according to RTOG 9005 guidelines (gold standard) and delivered in a single fraction of 24 Gy (\varnothing 1-2 cm), 18 Gy (\varnothing 2-3 cm) or 15 Gy (\varnothing 3-4 cm), respectively, adjusted according to tumor diameter (\varnothing). The dose is prescribed to the isodose line (50-80%) encompassing the metastasis with a safety margin of up to 1 mm depending on institution-specific accuracy.

Patients in the fractionated stereotactic radiotherapy group (experimental arm) will receive a total dose of 48 Gy in 12 daily fractions of 4 Gy each. An overall GTV-PTV safety margin of 2 mm will be used. The dose is prescribed to the 80% isodose line encompassing the PTV.

4.3. Randomization of subjects

Randomization is stratified according to metastasis volume ($< 14.1 \text{ cm}^3$, $\geq 14.1 \text{ cm}^3$) and primary tumor histology (radioresistant histology: melanoma, renal cell carcinoma and sarcoma vs. other). If multiple cerebral metastases are treated in the trial, the total volume of all treated metastases is used for stratification.

Randomization will be performed on patient level.

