In addition to the available retrospective evidence in larger brain metastases, the important dose-response relationship described by Wiggendaad and Zindler for brain metastases also predicts FSRT to be superior to SRS. Figure 1 shows the relationship between the delivered BED_{12-LQC} and local control at 12 months, as determined by Wiggendaad and

co-workers (Wiggenraad et al. 2011). The control arm will receive a BED_{12-LQC} of 36 Gy in a single fraction of 18 Gy, and the experimental arm will receive a BED_{12-LQC} of 62.8 Gy in multiple fractions (12 x 4 Gy fractionation scheme). Based on the dose-response relationship found by Wiggenraad and Zindler, this should result in a local control rate of 67.1% in the control arm and 85.8% in the experimental arm (Wiggenraad et al. 2011, Zindler et al. 2018) (Figure 1).

When combining the available retrospective evidence and the established relationship between dose and tumor control, a local control rate at 12 months of around 65% and 80% for SRS and FSRT, respectively serve as reasonable estimates for sample size calculation in a randomized trial.

This difference becomes even more clinically significant, as the number of treated brain metastases increases. For example, the probability of controlling all metastases in a patient with 4 brain metastases would be at least $(0.65)^4 = 17.9\%$ and could be increased to at least $(0.80)^4 = 41.0\%$.

Consequently, local control of brain metastases is an important endpoint.

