9.2. Sample size calculation

On the basis of available retrospective and dose-response relationship data, it is expected that SRS will result in a 12-month local tumor control rate of approximately 65% and that FSRT can increase this rate to about 80% (cf. Section 1.4). This difference is considered to be clinically significant. A sample size of N=191 evaluable cases each in the experimental and control arm, respectively, corresponding to a total of 382 patients, is required to detect a significant difference i.e. an increase in TTLP at least this large at 12-month follow-up in a randomized comparison. The number of TTLP events to be observed is 82. This calculation is based on the following framework conditions:

- The risk of making a false claim of superiority of FSRT which actually does not exist is 2.5% (α error, one-sided).
- The success rate for identifying superiority of FSRT over the control arm which actually exists is 80% (power, $1-\beta$ error).
- Assuming an exponential decline of TTLP curves
- As this is a basically palliative setting with disseminated disease, it must be considered that about half of the patients will be dead at 12-month follow-up. Consequently, a considerable proportion of patients

will have a truncated follow-up in which no event related to the primary endpoint occurs. The extent of this quasi-drop-out process is estimated to be $\leq 50\%$ and is also assumed to be exponentially distributed over the 12 months.

- Duration of follow-up for all patients: at least 12 months or until the incidence of local progression.

Note: Due to patient entry kinetics during the planned recruitment, and due to the intended follow-up period of up to 24 months for each patient (cf. section 5.1.4), the follow-up periods for a considerably number of patients, mainly those randomized early, may be significantly longer than 12 months by the end of the study. This should result in an increase in the expected number of observed events, leading to a further increase in power of the study. Since this effect is difficult to quantify (especially due to death as a competing risk event), it is not taken into account in sample size calculation, to be on the safe side. Therefore, the recruitment period is not included among the parameters provided above.

Sample size estimates were calculated based on the method of LACHIN and FOULKES (Lachin et al. 1986), applying the software NSURV (idv, Gauting, Germany).

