Time-to-event data such as time to local progression (TTLP), local progression-free survival (LPFS), and overall survival (OS) will be presented in life tables constructed using the KAPLAN-MEIER method (Kaplan et al. 1958) and compared using the log-rank test (Here, LPFS is defined like TTLP except that death not preceded by local progression will not be censored but counted as an event). If the assumption of "proportional hazards" underlying the Peto log rank test (Peto et al. 1972, Peto et al. 1976) clearly does not apply (Haybittle 1988), Gehan's generalized Wilcoxon test for comparing arbitrarily singly-censored samples will also be used as sensitivity analysis (Gehan 1965), preferably, as modified by Peto and co-workers and Prentice (Peto et al. 1972, Prentice 1978). Prospective stratification and other prognostic strata, if necessary, may be taken into account in further sensitivity analyses (Peto et al. 1976).

TTLP, the primary endpoint of the study, will be described and evaluated in another sensitivity analysis based on the cumulative incidence method (Gray 1988), in which death not associated with local progression will be treated as a competing risk event

Univariate consideration of prognostic factors will be performed by applying the above-mentioned methods accordingly. Multivariate analysis, if required, will be performed using the Cox proportional hazards regression model (Cox 1972).

Further details regarding the statistical analysis will be specified prospectively in a Statistical Analysis Plan before any analyses of treatment efficacy are carried out. As software, SPSS, R, TESTIMATE, and/or SQL will be used for analysis.

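### The stated 82 TTLP events do not follow from the sample size inputs (about 77 do), and the 65%/80% control rates are per-lesion in section 1.4 but per-patient in section 9.2

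*Protocol*

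**What the plan says.** **Endpoint.** Time to local progression (TTLP) is scored per patient. With several treated metastases, "progression is defined as at least one metastasis fulfilling the criteria for progression" (Protocol 1.6.1; sections 7.2 and 7.3 agree). Section 3.1 admits 1 to 10 brain metastases, with an indication for local radiotherapy of one or more measuring 1 to 4 cm.

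**Planning rates.** Section 9.2 expects that "SRS will result in a 12-month local tumor control rate of approximately 65% and that FSRT can increase this rate to about 80" per cent, and section 2.2 says the same. Section 1.4, where these rates are derived, raises both to the fourth power: "the probability of controlling all metastases in a patient with 4 brain metastases would be at least" 17.9% with 0.65 and 41.0% with 0.80.

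**Size.** Section 9.2 assumes one-sided 2.5% error, 80% power, exponential TTLP, exponential loss of up to 50% over 12 months (mainly deaths) and at least 12 months of follow-up, and cites the Lachin-Foulkes method. The result is 191 per arm, and "The number of TTLP events to be observed is 82".

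**Stratification and test.** Section 4.3 stratifies by histology and by metastasis volume (cut at 14.1 cm³): "If multiple cerebral metastases are treated in the trial, the total volume of all treated metastases is used for stratification". Section 9.4 makes the stratified log-rank test the main analysis of the primary endpoint. Later it adds: "Prospective stratification and other prognostic strata, if necessary, may be taken into account in further sensitivity analyses".

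**The concern.** There are two separate faults, and neither causes the other.

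1. The patient number and the event number should come from one set of inputs. The patient number does and the event number does not. Readers will use the event number to judge whether the trial delivered its planned information.

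2. The same two rates serve as lesion rates in one section and patient rates in another. Both uses cannot hold once patients with several treated lesions enter, because a patient with four lesions has four chances of an event. The expected event count then depends on a lesion-count mix that the protocol does not give.

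A related point is efficiency. By the reasoning of section 1.4, lesion count is strongly prognostic for this endpoint, yet it enters neither the randomization strata nor the main test directly.

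**Working it through.** **Inputs (section 9.2).** Yearly hazards: λS = −ln 0.65 = 0.4308; λF = −ln 0.80 = 0.2231; loss η = ln 2 = 0.6931 (50% at 12 months). Hazard ratio = 0.2231/0.4308 = 0.518, ln HR = −0.658.

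**Event probability by time T (years).** P(λ) = λ/(λ+η) × [1 − exp(−(λ+η)T)]. At T = 1:
- SRS: 0.4308/1.1239 × (1 − 0.325) = 0.2587
- FSRT: 0.2231/0.9163 × (1 − 0.400) = 0.1461
- average hazard 0.3270: 0.2050

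**Patient number (Lachin-Foulkes).** With φ(λ) = λ²/P(λ), φ is 0.7173 (SRS), 0.3408 (FSRT) and 0.5216 (average).
n per arm = [1.960·√(2 × 0.5216) + 0.8416·√(0.7173 + 0.3408)]² / (0.4308 − 0.2231)² = 190.7, so 191. The protocol's patient number is reproduced.

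**Expected events on the same inputs.** 191 × (0.2587 + 0.1461) = 77.3, or 2 × 191 × 0.2050 = 78.3 at the average hazard.

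**Required events.**
- Schoenfeld: 4 × (1.960 + 0.8416)²/0.658² = 72.6, so 73
- Freedman: (1.960 + 0.8416)² × (1.518/0.482)² = 77.8, so 78

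**Where could 82 come from?**
- Loss of 42% instead of 50% gives 82.3 events in 191 per arm, but the same formula then needs only about 179 per arm.
- Follow-up of 13 or 14 months gives 80.8 or 84.0 events.
- Uniform instead of exponential loss gives 80.3.

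No variant on the stated inputs gives both 191 and 82.

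**Consequence of 82.** Power = Φ(√82/2 × 0.658 − 1.960) = 84.6%, above the planned 80%.

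**Rates read per lesion, lesions independent.** A patient with k lesions has hazard kλ, so the hazard ratio stays 0.518 for every k, and required events stay at 73 to 78. Expected events rise. The protocol gives no lesion-count mix. Assume 60/20/10/5/5% of patients with 1/2/3/4/6 treated lesions. By 24 months (T = 2), if all 382 patients had k lesions, the formula gives 104.5, 168.3, 209.7, 238.1 and 274.1 events for k = 1, 2, 3, 4, 6. Weighted: 62.7 + 33.7 + 21.0 + 11.9 + 13.7 = 143.

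Simulated 12-month power under three other assumed mixes, with a log-rank test that ignores count, is 87%, 91% and 93%, against 82% with one lesion each.

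**Volume as a proxy for count (spheres, πd³/6).** Ten 1-cm lesions total 5.2 cm³ and three 2-cm lesions 12.6 cm³, both in the lower stratum. One 3-cm lesion is 14.14 cm³, in the upper stratum.

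**Gain from adding count (1, 2-3, ≥4) to volume stratification.** Simulated at 24 months with the 60/20/10/5/5% mix; lesion diameters are assumed.

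| Setting | Volume only | Volume and count |
|---|---|---|
| HR 0.52, independent, mostly small lesions | 94.0% | 96.1% |
| HR 0.52, independent, diameters uniform 1-4 cm | 94.9% | 97.0% |
| HR 0.65, independent, mostly small lesions | 68.6% | 72.9% |
| HR 0.65, independent, diameters uniform 1-4 cm | 67.8% | 72.6% |

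With a shared patient effect of variance 1 (assumed), the gain is about 1 point at HR 0.52 (76.4% to 77.4%) and about 2 at HR 0.65 (42.4% to 44.1%). Sampling error is about 1 point.

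**The case against.** The strongest reply is that nothing here invalidates the trial, and most of it stands.

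- The stratified log-rank test on a per-patient first event, randomized per patient, is valid without lesion count. Volume tracks count in part, section 9.4 allows adjusted sensitivity analyses, and the statistical analysis plan, which is not at hand, may name further covariates. Adding count is an efficiency gain, not a correction.
- Section 9.2 states bounds (loss of at most 50%, follow-up of at least 12 months), and 82 events can occur within them. This explains how 82 might be observed. It does not explain 82 as a design figure, because 191 per arm was computed at the bounds themselves.
- Section 1.4 says at least when it multiplies lesion rates, which allows positive correlation within a patient. That would shrink both the extra events and the gain from count.

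Three stronger readings are tempting but unsupported.

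- A reader might infer that reaching 82 events would end follow-up early. No section makes 82 a trigger for analysis or database closure. Follow-up runs to 24 months, and section 9.2 leaves the longer follow-up out of the calculation on purpose.
- A reader might infer a gain of about 8 points from lesion count (65% to 73% at HR 0.65). That compares with an unstratified test, which is not the planned one.
- A reader might take the later sentence in section 9.4 as demoting stratification to a sensitivity analysis. It closes a paragraph on time-to-event data generally and permits further analyses. The earlier statement on the primary endpoint is explicit and stands.

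**Conclusion.** The 82 events are not consistent with the protocol's own inputs, which give 191 per arm and about 77 events. The discrepancy is about 5 events and conservative.

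The unit of the 65%/80% rates is inconsistent between section 1.4 and sections 2.2 and 9.2. A reader might infer that the trial is therefore underpowered. With independent lesions the hazard ratio is unchanged, events increase and power stays above 80%. With a strong shared patient effect power can fall below 80%, but it does so even with one lesion per patient (66% at 12 months, variance 1), so the unit mismatch is not the cause.

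Adding lesion count gives a modest gain over the planned volume-stratified test: 1 to 2 points at HR 0.52, up to about 5 at HR 0.65 with independent lesions, less with correlation. HR 0.65 is not the planning effect. The 77 rests only on stated inputs. The 143 events and the power gains rest on assumed lesion counts and independence, and the gains also on assumed lesion sizes.

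**What to change.** 1. In sections 2.2 and 9.2, restate the event number as about 77 on the stated 12-month basis, or give the assumptions that yield 82 together with 191 per arm.
2. State whether 65% and 80% are lesion or patient rates. If lesion rates, give the expected events for a stated lesion-count mix.
3. Prespecify the number of treated metastases (for example 1, 2-3, ≥4) as a stratum or covariate in the stratified primary analysis. Keep the log-rank test stratified by the two randomization factors as a sensitivity analysis.

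The cost is wording and one corrected figure, with no additional patients; the treated-lesion count is already known. The downside is one more factor to prespecify and somewhat sparser strata, so the cut-points should be fixed before any efficacy analysis.
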